#### 4.1.3 Phase 1b FPT155 Monotherapy Dose Expansion

Enrollment in Phase 1b dose expansion will begin when the MTD and/or RD has been identified by the CRC. If additional cumulative safety or preliminary efficacy results from dose escalation or exploration suggest that an alternate dose or schedule may improve the benefit relative to risk in treatment with FPT155, more than one dose or schedule may be evaluated in the phase 1b cohorts.

Up to 8 tumor-specific cohorts consisting of approximately 30 patients each will evaluate the safety, efficacy, PK, and PD of FPT155 at a RD (see [Appendix 11](#)). Patients with advanced RCC and melanoma who have failed prior anti-PD(L)1 therapy will be enrolled in 2 of the 8 cohorts.

Additional tumor types for the remaining Phase 1b cohorts will be determined based on emerging safety, translational, and clinical data for FPT155, as well as any potential new safety signals from other immunotherapies, such as significant changes to prescribing information for approved immunotherapies.

Intensive monitoring will occur in the outpatient setting and include a minimum 6-hour observation window following completion of the first and second infusions. Additional monitoring requirements may be implemented based on emerging safety data from Phase 1a dose escalation.

**Table 7: Phase 1b Monotherapy Dose Expansion Cohorts and Tumor Types**

Cohort	Tumor Type
1	Renal cell carcinoma
2	Melanoma
3-8	Cohorts to be determined based on emerging safety, translational, and clinical data for FPT155, as well as any potential new safety signals from other immunotherapies, such as significant changes to prescribing information for approved immunotherapies (see Appendix 11 )

#### 4.1.4 Phase 1a FPT155+Pembrolizumab Dose Escalation

FPT155 will start at a dose level a minimum of 2 levels below that cleared in dose escalation with FPT155 monotherapy.

Dose escalation decisions will follow the standard 3+3 algorithm described above and continue up to the dose level established as the MTD for FPT155 monotherapy. Additional intermediate dose levels or dose regimens may be considered upon review of emerging safety, PK and PD results.

#### 4.1.5 FPT155 + Pembrolizumab Dose Exploration

Enrollment in combination dose exploration may occur at one more dose levels that have been cleared during combination dose escalation.

#### 4.1.6 Requirements for Archival Tumor Tissue and Fresh Biopsies

Dose Escalation (Monotherapy and FPT155 + pembrolizumab):

- Archival tumor tissue is required. If archival tumor tissue is not available, a fresh biopsy is required prior to treatment for retrospective biomarker analysis.
- Optional pre- and on-treatment biopsies will be requested during screening (prior to treatment) and during treatment (prior to the Cycle 3 Day 1 dose) to explore the relationship between baseline tumor immune phenotype and PD response.
- An additional optional biopsy will be requested at disease progression.

Dose Exploration/Expansion (Monotherapy and FPT155 + pembrolizumab):

- Archival tumor tissue is required for retrospective biomarker analysis. The fresh biopsy required at screening will be accepted in lieu of archival tumor tissue if archival tissue is not available.
- Pre- and on-treatment biopsies will be mandatory during screening (prior to treatment) and during treatment (prior to the Cycle 3 Day 1 dose) to explore the relationship between baseline tumor immune phenotype and PD response.
- An additional optional biopsy will be requested at disease progression.

#### 4.2 Study Treatment and Duration

FPT155 will be administered Q3W over approximately 60 minutes by IV infusion.

In combination with FPT155 and pembrolizumab, pembrolizumab will be administered a minimum of 30 minutes following completion of the FPT155 infusion. Pembrolizumab should be administered per the pembrolizumab Product Information.

Treatment is administered Q3W until disease progression, unacceptable toxicity, or patient withdrawal. If one drug is discontinued, treatment may continue with the other alone for up to an additional 12 months. Treatment beyond disease progression may be allowed in patients with initial RECIST v1.1 defined progressive disease if the criteria in Section 4.3 are met.

Patients should have end of treatment (EOT) follow-up visits approximately 28 days and 100 days after the last dose of treatment on study. In addition, patients enrolled in dose expansion will be followed for survival.

#### 4.3 Treatment Beyond Disease Progression

For patients in all cohorts, if progressive disease (based on RECIST v1.1) occurs, then the patient may continue to be treated with the scheduled regimen assigned after study enrollment until one of the following criteria is met:

- Confirmed disease progression: The assessment of disease progression by RECIST v1.1 (baseline disease progression assessment) will be confirmed by a repeat evaluation at the next tumor assessment time point, but no sooner than 4 weeks later. If any subsequent tumor assessment time point demonstrates disease progression by RECIST v1.1 or demonstrates further increase in the overall tumor burden (the sum of diameters of target lesions and new lesions), when compared to the baseline disease progression assessment (the sum of diameters of target lesions or the presence of a new lesion), then the subject would be deemed as having confirmed disease progression.
- Meets any of the investigational product discontinuation criteria.
- Clinical symptoms or signs indicating clinically significant disease progression such that the benefit-risk ratio of continuing therapy is no longer justified.
- Rapid disease progression or threat to vital organs/critical anatomical sites (eg, spinal cord compression) requiring urgent alternative medical intervention, and/or continuation of study therapy would prevent institution of such intervention.

#### 4.4 End of Study Definition

The EOT follow-up visit approximately 100 days after the last dose of treatment on study will be considered the end of the study in Phase 1a.

In the Phase 1b portion of the study, patients will also be followed for survival by clinic visit or by telephone approximately every 3 months after the Day 100 EOT visit. Death, loss to follow-up, or withdrawal of consent of the last study subject, or study termination by the Sponsor (whichever occurs first), will be considered the end of the study in Phase 1b.

#### 4.5 Scientific Rationale for Study Design

The study is designed as an initial accelerated titration followed by a standard 3+3 dose escalation. The initial accelerated titration component may reduce the number of patients receiving potentially subtherapeutic doses of the study drug. The 3+3 design is chosen to avoid selection of a Phase 2 clinical trial dose that causes a treatment-limiting toxicity in more than 17% of patients, which is a standard that has been considered acceptable as an outpatient therapeutic for patients with limited options and life-threatening disease. This design has the advantage of being rule-based, allocates the lowest dose level to the first cohort, and adaptively escalates/de-escalates based on observed DLTs. Its execution is straightforward and generally well understood by clinicians and investigators, decreasing the potential for deviations from protocol.

Phase 1a dose exploration with mandatory pre- and on-treatment biopsies at doses  $\leq$  MTD will provide additional insight into the safety, PK, PD and mechanism of action of FPT155 and may help in determining the RD for Phase 1b.

Phase 1b for FPT155 monotherapy includes up to 8 tumor-specific cohorts. Patients with advanced RCC and melanoma that have failed prior anti-PD(L)1 therapy will be enrolled in 2 of the 8 cohorts. These patients have a poor prognosis and enrolling them will enable evaluation of the clinical activity of FPT155 in these typically immune-competent tumors that have progressed on a checkpoint inhibitor. Additional tumor types for the remaining 6 Phase 1b cohorts ([Appendix 11](#)) will be determined based on emerging safety, translational, and clinical data for FPT155, as well as any potential new safety signals from other immunotherapies, such as significant changes to prescribing information for approved immunotherapies.

Combination dose escalation with FPT155 and pembrolizumab will start with a FPT155 dose that is a minimum of two dose levels lower than the highest dose cleared during evaluation of FPT155 monotherapy as outlined below in [Table 8](#). Additional patients may be added in combination dose exploration at one or more dose levels that are cleared during combination dose escalation to better characterize the safety profile and preliminary clinical activity. The combination will be limited to patients with non-small cell lung cancer to maximize on the ability to interpret results from the limited enrollment that is planned.

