#### 4.1.1.3 Dose Limiting Toxicity Definitions

The DLT evaluation interval begins on the first day of treatment upon start of infusion and continues for 21 days. Patients who receive at least 1 dose of study treatment and remain on study for the 21-day DLT evaluation interval or patients who discontinue study treatment for drug-related AEs before clearing the 21-day DLT evaluation interval will be considered evaluable for DLT determination.

DLTs during Phase 1a dose escalation are defined as any of the following deemed by the investigator as related to FPT155:

- Absolute neutrophil count (ANC)  $< 1.0 \times 10^9/L$  for  $> 5$  days duration or Grade 3 febrile neutropenia (eg, ANC  $< 1.0 \times 10^9/L$  with a single temperature of  $> 38.3^{\circ}C$  or fever  $> 38^{\circ}C$  for more than 1 hour)
- Platelets  $< 25 \times 10^9/L$  or platelets  $< 50 \times 10^9/L$  with clinically significant hemorrhage
- Aspartate aminotransferase (AST) or ALT  $> 3 \times$  upper limit of normal (ULN) with concomitant total bilirubin  $> 2 \times$  ULN not related to liver involvement with cancer
- Grade 3-4 non-hematological toxicity except:
  - Grade 3 fatigue  $< 7$  days
  - Grade 3 nausea and Grade 3-4 vomiting and diarrhea lasting  $< 72$  hours in patients who have not received optimal anti-emetic and/or anti-diarrheal therapy
  - Grade 3 endocrinopathy that is adequately treated by hormone replacement
  - Laboratory value that may be corrected through replacement within 48 hours
- Grade 2 neurological toxicity except headache and peripheral neuropathy in patients with Grade 1-2 peripheral neuropathy at entry

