#### Additional DLT Considerations for FPT155 in combination with pembrolizumab

Because pembrolizumab is a known immune checkpoint inhibitor and one of the proposed mechanisms of action of FPT155 is immune checkpoint blockade, immune-related adverse events (irAEs) are anticipated with this combination. An irAE is defined as a clinically significant AE that is associated with study drug exposure, without a clear alternate cause, and consistent with an immune-mediated mechanism. Based on that background, the first occurrence of the following irAEs will not be considered a DLT because they may occur with immune therapy and are likely to be fully reversible per [Appendix 8](#):

- Grade 3 tumor flare (defined as local pain, irritation, or rash localized at sites of known or suspected tumor)
- Grade 3 non-skin immune-related adverse event (irAE) that resolve to a Grade 1 or less within 14 days with management per [Appendix 8](#)
- Transient (resolving within 6 hours of onset) Grade 3 infusion-related AEs
- Grade 3 drug-related bronchospasm or anaphylactic or anaphylactoid reactions

Dose escalation may be paused prior to determining an MTD based on observed safety, tolerability, or emerging PK or PD results.

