**Table 6: Algorithm for 3+3 Dose Escalation Decisions**

Number of Patients with DLT at a Given Dose Level	Dose Escalation Decision Rule
0/3 or 1/6	Enroll 3 patients at next dose level (next/higher cohort)
1/3	Enroll 3 additional patients at current dose level (current cohort)
$\geq 2$	Stop enrollment. If at the starting dose level, the study will be stopped. If at any other dose level, enroll 3 more patients at the previous dose level (previous/lower cohort) if only 3 were previously enrolled, or at an intermediate dose level

Abbreviations: DLT = dose limiting toxicity.

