#### 4.1.1.6 Determination of Recommended Dose and Maximum Tolerated Dose

The maximum tolerated dose (MTD) will be defined as the dose level below that in which  $\geq 2$  DLTs are identified. If dose escalation completes without the identification of 2 DLTs at a given dose level, no MTD will have been identified. The Sponsor may discontinue dose escalation prior to determining a MTD based on the available observed safety, tolerability, PK and PD. The RD of FPT155 will be identified based on an evaluation of all available safety, tolerability, PK, and PD data. The determination of RD will consider toxicities observed both during and beyond the DLT evaluation period as well as dose reductions and discontinuations due to toxicity that do not meet the DLT criteria. The RD, therefore, may or may not be the same as the MTD but cannot be higher than the MTD.

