### 3. Recording an AE and/or SAE

AE and SAE Recording

The investigator will record all available relevant AE/SAE information in the CRF and send it to the sponsor or designee within 24 hours of becoming aware of the event.
 
There may be instances when copies of medical records for certain cases are requested by the Sponsor. In this case, all patient identifiers, with the exception of the patient number, will be redacted on the copies of the medical records before submission.
 
The investigator will attempt to establish a diagnosis of the event based on signs, symptoms, and/or other clinical information. Whenever possible, the diagnosis (not the individual signs/symptoms) will be documented as the AE/SAE.

Assessment of Intensity

Investigators need to assess the severity of AEs according to the guidelines provided in NCI-CTCAE, version 4.03. CTCAE v 4.03 Severity Grades are:
 
Grade 1: Mild; asymptomatic or mild symptoms; clinical or diagnostic observations only; intervention not indicated; mild AE
 
Grade 2: Moderate; minimal, local or non-invasive intervention indicated; limiting age-appropriate instrumental activities of daily living; moderate AE
 
Grade 3: Severe or medically significant but non-immediately life-threatening; hospitalization or prolongation of hospitalization indicated; disabling; limiting self-care activities of daily living; severe AE
 
Grade 4: Life-threatening consequences; urgent intervention indicated
 
Grade 5: Fatal AE
 
If the AE is not specified in the CTCAE or the study protocol, the grading of severity will be assessed as mild (Grade 1), moderate (Grade 2), severe (Grade 3), life-threatening (Grade 4), or death due to the AE (Grade 5) using the following definitions:
 
Mild: The patient is aware of the event or symptom, but the event or symptom is easily tolerated.
 
Moderate: The patient experiences sufficient discomfort to interfere with or reduce his or her usual level of activity.
 
Severe: Significant impairment of functioning; the patient is unable to carry out usual activities.
 
Very severe (life-threatening): The patient's life is at risk from the event.

Assessment of Causality

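### Section 4.5 credits the 3+3 with a 17% toxicity ceiling it does not have; the non-hematological DLT criterion omits Grade 5, and DLT-evaluability is defined in two ways

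*Protocol*

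**What the plan says.** **Rationale.** Protocol Section 4.5 states: "The 3+3 design is chosen to avoid selection of a Phase 2 clinical trial dose that causes a treatment-limiting toxicity in more than 17" percent of patients. It describes this as an accepted standard for the population. It gives no derivation, no assumed true rates and no operating characteristics.

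**Escalation rule.** In Table 6 of the protocol (Table 2 of the SAP), a result of 0/3 or 1/6 leads to "Enroll 3 patients at next dose level (next/higher cohort". A result of 1/3 adds three patients at the same level. Two or more DLTs stop the level; the level below is then topped up by three if it had only three patients, or an intermediate level is tried. Section 4.1.1.6 defines the MTD as the level below the one with at least two DLTs and caps the RD at the MTD. It adds: "The determination of RD will consider toxicities observed both during and beyond the DLT evaluation period".

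**DLT criterion.** Protocol Section 4.1.1.3, the synopsis and SAP 2.2.1 all word the non-hematological item as "Grade 3-4 non-hematological toxicity except", followed by a list of exceptions. The severity scales in Protocol Appendix 2 and SAP 6.3.1.2 both include "Grade 5: Fatal AE".

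**Evaluability.** Section 4.1.1.3 counts "Patients who receive at least 1 dose of study treatment and remain on study for the 21-day DLT evaluation interval" and also says "patients who discontinue study treatment for drug-related AEs before clearing the 21-day DLT evaluation interval will be considered evaluable for DLT determination". Section 7.4 bases replacement on that definition. Section 9.3 and SAP 4.3 instead require a dose of every assigned drug plus 21 days on study, or a DLT within the interval. SAP 6.3 and 6.3.1.7 use this second version for the DLT table. In the combination cohorts, the first occurrence of certain events is exempt from DLT status, among them "Transient (resolving within 6 hours of onset) Grade 3 infusion-related AEs".

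**The concern.** DLT incidence is a primary Phase 1a endpoint. The Table 6 count governs monotherapy escalation to 840 and 1260 mg and all combination escalation.

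First, Section 4.5 reads as though the rule keeps the true toxicity rate of the chosen dose at or below 17%. A rule based on three or six patients cannot do that, so an ethics committee or investigator is offered more assurance than the design gives.

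Second, the written non-hematological criterion leaves out the worst grade, although the MTD is defined by counting events that meet the written criteria.

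Third, the decision count and the reported DLT table can rest on different patients, because each uses its own definition of evaluable.

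**Working it through.** **1. Source of the 17%.** 1/6 = 16.7%, which rounds to 17%. It is the largest observed DLT fraction that still clears a level in Table 6. The protocol does not derive the figure, so this link is an inference, but nothing else in the design produces it.

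**2. Chance that a tested level clears Table 6.** Let p be the true DLT rate; its values below are assumptions, shown as a range. A level clears on 0/3, or on 1/3 followed by 0/3:

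P(clear) = (1−p)³ + 3p(1−p)² × (1−p)³

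If the level is filled to six patients, it clears with at most one DLT:

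P(≤1 of 6) = (1−p)⁶ + 6p(1−p)⁵

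| True DLT rate p | Table 6 as run | Filled to six |
|---|---|---|
| 17% | 0.572 + 0.201 = 0.773 | 0.327 + 0.402 = 0.729 |
| 25% | 0.422 + 0.178 = 0.600 | 0.178 + 0.356 = 0.534 |
| 30% | 0.343 + 0.151 = 0.494 | 0.118 + 0.303 = 0.420 |
| 40% | 0.216 + 0.093 = 0.309 | 0.047 + 0.187 = 0.233 |

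A simulation of the Table 6 rule at p = 30% (400,000 runs) gave 0.4935, in agreement.

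Solving the same formulas for p, the clearing probability falls to 50% only at a true rate of 29.7% (26.4% with six) and to 10% only at 57.6% (51.0% with six). One-sided 95% Clopper-Pearson upper bounds lead to the same conclusion: 63% after 0/3 and 58% after 1/6.

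**3. Grade 5.** The grading scale runs to 5, while the criterion stops at 4. No other DLT item names Grade 5 or death. The rule in Section 6.9.3 that treats a dose reduction in the DLT period as a DLT does not reach a fatal event. Read literally, a related non-hematological event recorded only as Grade 5 is not a DLT. If that patient dies before Day 21, the patient has neither stayed on study for 21 days nor had a listed DLT, and so falls outside the population in Section 9.3 and SAP 4.3.

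**4. Evaluability, side by side.**

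| Patient | Section 4.1.1.3 | Section 9.3 / SAP 4.3 |
|---|---|---|
| Stops treatment, stays on study to Day 21, received all assigned drugs | Evaluable | Evaluable |
| Stops for a related AE that is not a DLT and leaves the study before Day 21 | Evaluable | Not evaluable |
| Combination: exempt Grade 3 infusion event, FPT155 stopped, pembrolizumab never given | Evaluable | Not evaluable |

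The third row can arise from the protocol's own rules. The exemption covers a first Grade 3 infusion event resolving within 6 hours. Section 6.9.6.1 requires permanent discontinuation of FPT155 when such an event lasts more than 4 hours. An event lasting between 4 and 6 hours therefore ends FPT155 without being a DLT. If pembrolizumab is then not given, the patient counts toward 0/3 for escalation but does not appear in the DLT table.

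**The case against.** **The 49% is not a selection probability, and nothing in the plan is miscalculated.** This is correct. The figures are per-level clearing probabilities under assumed true rates, and 1/6 is properly rounded to 17%. Choosing the RD also draws on later toxicity, PK and PD, and on up to about 50 dose-exploration patients. The 560 mg RD was endorsed after review of 10 patients at 280 mg and 7 at 560 mg, with no DLTs in escalation (Appendix 11). These points reduce the practical effect. They do not rescue the sentence, because Section 4.5 attributes the 17% to the 3+3 itself. Reading the sentence as an aim rather than a guarantee still leaves a design whose rule clears a level at a 30% true rate about half the time.

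**A related death would not be ignored.** Escalation rests on overall safety as well as DLTs and needs agreement of the Cohort Review Committee (Section 4.1.1), and deaths are tabulated separately (SAP 6.3.2). Many fatal toxicities would also have met the criterion at Grade 3 or 4 first. All of this stands. What remains is a gap in the written rule and in the DLT table for an event recorded only as Grade 5.

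**The evaluability texts can be reconciled.** Section 6.0 defines the combination study interventions as both drugs, so one dose of study treatment could be read as a dose of each. That may answer the first limb of Section 4.1.1.3. It does not answer the second limb, under which stopping for a related AE is enough. It is also true that an infusion event resolving within 4 hours may allow a restart, so the mismatch is confined to few patients.

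**Conclusion.** The concern holds on all three points. The 17% in Section 4.5 is an observed cut-off presented as a limit on toxicity in patients. Across assumed true DLT rates of 17% to 40%, a tested level clears with probability 77% down to 31% (73% down to 23% with six patients). The calculation assumes independent patients with a common DLT rate at that level, and describes clearing rather than final selection.

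The Grade 5 omission and the evaluability mismatch follow from the wording alone. They would affect few patients and are not quantified. No DLTs were reported in monotherapy escalation through 560 mg, so nothing here shows that a past decision was wrong. The importance is moderate: the text should be corrected before it governs 840 mg, 1260 mg and the combination cohorts.

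**What to change.** 1. **Section 4.5.** Replace the 17% sentence with: *The 3+3 escalates when the observed DLT proportion is at most 1/6; a tested level clears with probability 77%, 60%, 49% and 31% at true DLT rates of 17%, 25%, 30% and 40%; RD selection also uses toxicity beyond the DLT period.*
2. **Section 4.1.1.3, synopsis and SAP 2.2.1.** Change the item to: *Grade 3 or higher non-hematological toxicity (including Grade 5) except:* and keep the listed exceptions. A related fatal event in the window then counts as a DLT and brings the patient into the Section 9.3 population.
3. **Section 4.1.1.3, synopsis and Section 7.4.** Use the DLT-evaluable definition of Section 9.3 and SAP 4.3 for escalation, replacement and reporting alike.

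No new data or tables are needed. The stated assurance becomes less favourable. Item 3 changes who is replaced in an ongoing escalation, so an occasional extra patient may be enrolled. Item 2 alters a safety criterion after 11 dose levels were assessed under the current wording, so the amendment should say from which level it applies.
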